- Adult (>18 years of age and older) patients who have or will have undergone surgical resection or biopsy of a supratentorial brain tumor and are able to consent for themselves. During the informed consent process subjects with perceived cognitive disability will be excluded from study participation.
- Able to be randomized prior to or up to 48 hours after surgery.

Exclusion criteria -

- Known history of seizure activity
- Pregnant or breastfeeding
- Renal dysfunction (CrCl<30ml/min)
- Beck's Depression Inventory (BDI) ≥14.(Subjects will have the BDI administered at baseline visit, prior to randomization. Those who score ≥14, will be excluded from the study and referred to clinical psychology. Subjects who select "2" or "3" on question 9, will be referred to clinical psychology without regard to the overall total score.)
- Allergy to levetiracetam

Research Plan:

After obtaining informed consent, subjects will be randomized into one of the following arms to receive study drug as follows:

- 1) Levetiracetam (Keppra at a daily dose of 1000mg (administered as one 500 mg tablet)PO twice daily for one (1) week.
- 2) Levetiracetam (Keppra) at a daily dose of 1000mg (administered as one 500 mg tablet)PO twice daily for six (6) weeks.

A simple randomization scheme will be used and will be generated by our statistician. All patients will be weaned off of the AED over 2 days by decreasing the dose to 500mg po every day for 2 days and then stop. The taper is to commence at day 5 for the one week group and at 2 days prior to the stop date for the 6 week group. The taper will be included on their prescription instructions and in the patient's discharge instructions to ensure proper taper of the drug. As is protocol, patients are given verbal instructions of all of their discharge medications prior to discharge along with a "teach back" method to confirm they understand how to take and stop their medications when they go home. Patients will begin study medication 48 hours post-op, regardless if they are discharged or remain hospitalized. At discharge, they will continue the medication regimen for the amount of time they were randomized.

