Participants will maintain a diary that will collect seizure occurrences and daily medication intake. The RedCap database will be used to collect patient data. Participants will also complete the Beck Depression Inventory (BDI) and Neurotoxicity Scale⁷ to assess mood changes and level of cognitive functioning at baseline (preoperatively or 24-48hrs postoperatively) and at 6 weeks postoperatively. Patients with a BDI score suggestive of mild mood disturbance or depression (BDI score \geq 14) will be further evaluated by the Principal Investigator. This evaluation may include discontinuing leveteracitam, the initiation of antidepressant medications, or referral to clinical psychology. Patients will be followed until study completion and study activities will be conducted per the following Table of Events.

Activity	Baseline	Study Completion**
	(24-48 hours post-op)	6 weeks postop (+/- 4days)
Inclusion/exclusion criteria	X	
Informed consent	X	
Dispense prescription	X	
Dispense diary	X	
Collect or record diary data		X
Beck Depression Inventory (BDI)	X	X
Neurotoxicity Scale	X	X

^{**}May be completed during a routine office visit or by telephone

Data will be collected by the clinical trial coordinator and kept in an encrypted and password protected database in the coordinator's locked office. Only the investigators and study coordinator will have access to the data with identifiers. At the conclusion of the study, the data will be deidentifed and the key will be kept in a secure location in the coordinator's locked office. The key will be kept until the study is completed and the manuscript is accepted for publication.

Subjects will be assigned a unique ID number and the following data points will be captured in the RedCap database:

- Unique study ID number
- Complete past medical and surgical history
- Family history of seizures
- Tumor pathology results
- Tumor imaging findings
- Concomitant Medications
- Neurotoxicity scale scores
- BDI scores
- Seizure Diary responses

• Records of side effects or symptoms experienced

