Adverse events will be collected by the study coordinator at the six week evaluation or sooner if the patient contacts their physician/study team about new symptoms/problems. These events will be documented in the RedCap database. To ensure subject safety, each adverse event will be reviewed by an independent medical monitor ([name]) to determine if it is treatment-related. After each treatment-related adverse event that is "Serious and probable" or "Serious and definite" is identified, the study statistician will use a dynamic sequential testing method to determine if the proportion of enrolled patients who have experienced these types of adverse events up to that time has statistically exceeded a maximum acceptable proportion of 10%8. This method employs a concave alpha-spending function that allows a greater chance of detecting an unacceptably high adverse event rate earlier in the study while maintaining a nominal one-sided Type I error rate of 10% over the entire sequence of tests. Using a similar sequential testing approach, the odds ratio for experiencing a treatment-related adverse event between the two arms of the study will be tested for difference from 1 .after each adverse event, at a nominal two-sided sequence-wide Type I error rate of 20%. If either the maximum acceptable adverse event rate is exceeded, or odds ratio foradverse events between the 2 study arms is found to differ from one, study enrollment will be stopped for further evaluation of patient safety.

At the completion of the study, the scores on the neurotoxicity scale will be compared between the two groups. The analysis will be performed in an intent-to-treat manner. The groups will be compared using the Mann-Whitney test for the neurotoxicity scores and Fisher's exact test for the seizure rates. Using the neurotoxicity scale, we will need 38 patients in each group to show a difference of 5.4 points in the scale with a power of 80%. The maximum score on the scale is 81^7 .

Possible discomforts or risks: Study participants may suffer from seizures related to their brain tumor or demonstrate side effects from using levetiracetam which may include:

Version Date: 30 October 2019

Sleepiness

Weakness

Infection

Dizziness

Other possible risks of levetiracetam may include:

Mood and behavior changes such as aggression, agitation, anger, anxiety, apathy,

mood swings, depression, hostility, irritability and psychotic symptoms

Hallucinations delusions and unusual behavior.

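### Does closing the seizure count at the six-week visit bias Fisher's test against the one-week arm?

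*Combined protocol and SAP*

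**What the plan says.** Seizures are a secondary endpoint. The Secondary Objectives ask whether seizure rates are related to a shorter or longer course. The analysis paragraph of the Research Plan applies Fisher's exact test to those rates by intention to treat and gives no counting window.

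The data come from a participant diary. The Table of Events has the diary handed out in the Baseline column, headed 24-48 hours after surgery. The row "Collect or record diary data" is marked only under Study Completion, which is timed at "6 weeks postop (+/- 4days" days. Follow-up goes no further: "Patients will be followed until study completion and study activities will be conducted per the following Table of Events". Adverse events follow the same clock: "Adverse events will be collected by the study coordinator at the six week evaluation or sooner".

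On treatment, the Research Plan says "Patients will begin study medication 48 hours post-op, regardless if they are discharged or remain hospitalized", and then "At discharge, they will continue the medication regimen for the amount of time they were randomized". On stopping, it says "All patients will be weaned off of the AED over 2 days". The taper begins at day 5 in the one-week arm and "at 2 days prior to the stop date for the 6 week group". The origin of the day count is not stated.

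The text above the table allows the baseline mood and neurotoxicity questionnaires before surgery or at 24-48 hours after it. The inclusion criteria allow randomization before surgery. The table's baseline heading gives only the post-operative option.

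**The concern.** Both arms are weaned off the drug, but the count closes at about the time the six-week arm stops. The taper and roughly a month off drug always fall inside the count for the one-week arm. For the six-week arm, many allowed visit days come before the taper has even begun. If stopping levetiracetam carried the same seizure risk whenever it happened, the diary would record that risk in one arm and miss it in the other. Fisher's test would then lean one way, against the shortened course.

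This could matter to readers. The Abstract says that the trial is meant to inform neurosurgical guidelines, and any neurotoxicity benefit of the short course will be weighed against its seizure count. The start of the count is not spelled out either, because the table heading and the text differ on when baseline may take place.

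**Working it through.** **Inputs.** Visit at 42 ± 4 days after surgery (Table of Events). First dose at 48 hours, i.e. day 2; courses of 7 and 42 days; two-day taper ending at the stop (Research Plan).

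**Close of the count.** 42 − 4 = day 38 to 42 + 4 = day 46, which is 9 allowed visit days, the same in both arms.

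**Days off drug = visit day − stop day, not below 0.**

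| Course counted from | Stop, one-week | Stop, six-week | Off drug, one-week | Off drug, six-week |
|---|---|---|---|---|
| First dose | 2 + 7 = 9 | 2 + 42 = 44 | 38 − 9 = 29 to 46 − 9 = 37 | 0 to 46 − 44 = 2 |
| Surgery | 7 | 42 | 38 − 7 = 31 to 46 − 7 = 39 | 0 to 46 − 42 = 4 |

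At a day-42 visit the figures are 33 or 35 days against 0.

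**Where the visit falls in the six-week arm.** From first dose, the taper starts on day 42: 4 of the 9 visit days precede it, 2 fall within it, and 3 fall on or after the stop. From surgery, the taper starts on day 40: the split is 2, 2 and 5. The asymmetry in time off drug is therefore real under either reading.

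**Effect on Fisher's test.** The documents give no seizure rate after stopping, so the following are assumptions: 38 per arm (the plan's sample size for the neurotoxicity scale); b = 5% of patients with a seizure counted in either arm; the same share w in each arm with a seizure in the 14 days after stopping, spread evenly; f = the fraction of those 14 days inside the six-week arm's count. Then

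- one-week arm: p1 = 1 − (1 − b)(1 − w)
- six-week arm: p2 = 1 − (1 − b)(1 − wf)

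For a day-42 visit, f = 0. With w = 5%, p1 = 1 − 0.95 × 0.95 = 0.0975 and p2 = 0.05, so 38 × 0.0975 = 3.7 against 38 × 0.05 = 1.9 expected patients. Enumerating all tables at two-sided 0.05:

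| w | Expected patients, day 42 | P(p<0.05), day 42 | P(p<0.05), day 46 from surgery (f = 4/14) | P(p<0.05), both periods fully counted |
|---|---|---|---|---|
| 5% | 3.7 vs 1.9 | 3.4% | 2.3% | 1.5% |
| 10% | 5.5 vs 1.9 | 14.7% | 7.5% | 2.3% |
| 20% | 9.1 vs 1.9 | 56.6% | 25.5% | 2.8% |

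Significance needs at least 6 against 0, or 9 against 2. At a day-42 visit, with b from 0 to 10% and w up to 5%, the probability never exceeds 4.3%.

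**Would the obvious remedies help?**

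- *Cut the count at day 38.* Time off drug becomes 29 or 31 days against exactly 0, and up to 46 − 38 = 8 days of diary data are lost. The imbalance is complete and only relabelled.
- *Telephone the six-week arm 14 days after its stop.* Contact would fall on day 42 + 14 = 56 or 44 + 14 = 58. Surveillance in that arm would run 56 − 46 = 10 to 58 − 38 = 20 days longer than in the other.
- *Align the arms on days since stopping.* With stops on days 9 and 44, this sets days 9-23 after surgery against days 44-58. The Background reports post-craniotomy seizures in the first week in up to 35% of patients, so time since surgery cannot be ignored.

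**The case for a change.** The strongest case for a change is that a course includes its end. A trial comparing course lengths should see what happens when each course stops, and here one stop is observed in full while the other is hardly observed. No passage says that the comparison is meant to be mostly off drug against on drug. At w = 10% the chance of a significant result rises from 2.3% to 14.7%, nearly all of it against the short course, and even at w = 5% it more than doubles. One telephone call is cheap, and completion by telephone is already allowed.

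The description is correct and stands: the plan cannot show seizure risk after the six-week course ends. The inference to bias does not stand. More seizures in the arm that stops earlier would be a genuine effect of assignment over the period observed. It becomes an error only if the Secondary Objectives are read as asking about complete courses with equal time after each stop, which they do not say. Equal risk after stopping on day 9 and day 44 is also an assumption without support in the documents. A call on the same post-operative day in both arms would be sound, but it would add data for a further question and would not repair the present one.

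**Conclusion.** No change to the plan is needed. Every patient is followed from surgery to the same visit and analysed as randomized, so the seizure comparison is a valid one over about six weeks after surgery. Closing there is a fair trade-off: it keeps follow-up equal, at the price of not observing the end of the longer course. An analyst would naturally take the window as the diary period and report the result on those terms, not as seizure risk after both courses are complete.

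The open start is a small gap. The diary row implies a start at the baseline contact, and any ambiguity for patients randomized before surgery applies to both arms alike. It plays no part in the 29-39 against 0-4 day contrast, which pools two readings of the day count. The Research Plan and Table of Events should be reconciled on that origin and on the baseline heading. This is clerical, it moves the figures by two days, and I take no view on which reading is right.

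The size rests wholly on assumed rates. At w = 5% or below (with b = 5%) the gap is under 2 expected patients. The plan excludes patients with a known seizure history, and the Background cites one trial with a low post-operative incidence, so the small end is plausible but not established. The 56.6% figure would require one in five such patients to have a seizure within 14 days of stopping. The primary neurotoxicity analysis is not affected.

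### Adverse events are solicited only at week 6 and the diary is not described as recording symptoms, so milder on-drug events are likely to be under-captured more in the 1-week arm

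*Combined protocol and SAP*

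**What the plan says.** All references are to the combined protocol and SAP.

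- **Collection of adverse events (Research Plan).** "Adverse events will be collected by the study coordinator at the six week evaluation or sooner if the patient contacts their physician/study team". Patient-initiated reports are therefore accepted at any time, but the only occasion on which the team asks is week 6.
- **Schedule (Table of Events).** There are two columns: baseline, and study completion at six weeks after surgery with a window of 4 days either way. There is no adverse-event row and no contact near the end of the 1-week course. The final contact "May be completed during a routine office visit or by telephone".
- **Diary (Research Plan).** "Participants will maintain a diary that will collect seizure occurrences and daily medication intake". The Table of Events has it collected or recorded only at study completion.
- **Database list (Research Plan).** One item is "Records of side effects or symptoms experienced", with no timing or collection tool attached.
- **Dosing periods (Research Plan).** "Patients will begin study medication 48 hours post-op, regardless if they are discharged or remain hospitalized". The arms take drug "PO twice daily for one (1) week" or "PO twice daily for six (6) weeks".
- **Use of the data.** The Abstract names adverse events as a secondary endpoint. The Research Plan has two sequential safety tests. One compares the pooled proportion of patients with serious events judged probably or definitely related against 10%. The other tests the between-arm odds ratio for any treatment-related event, after each event, at a two-sided sequence-wide error rate of 20%.

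**The concern.** The two arms are asked the same question on the same day, but their on-drug time stands at different distances from that day. In the 1-week arm all of it is remote. In the 6-week arm some is equally remote and some is current. If patients forget milder symptoms over time, the loss differs by arm.

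The common effects in the risk section (sleepiness, weakness, dizziness) are of the kind that can pass without a call to the clinic. Under-capture in the 1-week arm points the same way as the expectation under Possible Benefits that the short course may bring fewer side effects. It also moves the monitored odds ratio in the direction of a worse 6-week arm. The medical monitor must judge relatedness, and in the 1-week arm that depends partly on whether onset fell inside a seven-day window. No onset date is described as being recorded at the time.

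**Working it through.** The plan gives no figure for the recall interval or for completeness of capture, so there is nothing to reproduce. The check has three parts.

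**1. Date arithmetic (inputs from the Research Plan and Table of Events).** Drug starts on day 2. It ends on day 2 + 7 = 9 in the 1-week arm and day 2 + 42 = 44 in the 6-week arm. The visit is on day 42, window 38 to 46.

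- 1-week arm: the last on-drug day is 42 − 9 = 33 days back and the first is 42 − 2 = 40 days back. Over the visit window the last on-drug day is 29 to 37 days back.
- 6-week arm: at a day-42 visit, on-drug time runs from 40 days back to 0. Over the window the visit falls between 6 days before and 2 days after day 44.
- If dosing were counted from surgery instead, the last on-drug day in the 1-week arm would be 35 days back (31 to 39).

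**2. Relative capture of on-drug events (recall model assumed; not in the documents).** Let the chance of recalling an event at lag t days be exp(−kt), with k = ln 2 / h for half-life h. Mean recall over lags a to b is

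c(a, b) = [exp(−ka) − exp(−kb)] / [k(b − a)].

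With uniform onset on drug, no self-reporting and a day-42 visit, use c(33, 40) for the 1-week arm and c(0, 40) for the 6-week arm. For h = 28 days, k = 0.02476:

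- c(33, 40) = (0.4418 − 0.3715) / (0.02476 × 7) = 0.41
- c(0, 40) = (1 − 0.3715) / (0.02476 × 40) = 0.63
- ratio = 1.6

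Two further inputs are equally unknown: the share of events self-reported promptly, and when onset occurs in the 6-week arm. With half self-reported, each capture becomes 0.5 + 0.5c; for h = 28 days the ratio is 0.817 / 0.703 = 1.16. With half of 6-week-arm onsets in week 1 and the rest spread evenly afterwards, its capture is 0.5c(33, 40) + 0.5c(0, 33).

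| Assumption | h = 2 wk | h = 4 wk | h = 8 wk |
|---|---|---|---|
| Capture, 1-week arm (no self-report) | 16% | 41% | 64% |
| Capture, 6-week arm (uniform onset, no self-report) | 44% | 63% | 79% |
| Ratio: uniform onset, no self-report | 2.6 | 1.6 | 1.2 |
| Ratio: half of onsets in week 1, no self-report | 2.0 | 1.3 | 1.1 |
| Ratio: uniform onset, half self-reported | 1.23 | 1.16 | 1.09 |
| Ratio: both of the above | 1.14 | 1.10 | 1.06 |
| Ratio: all onset in week 1 | 1.0 | 1.0 | 1.0 |

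**3. Odds-ratio scale (separate illustration, all inputs assumed).** Take equal true per-patient risk p in both arms and 90% capture in the 6-week arm. With p = 0.20 and 70% capture in the 1-week arm, the observed odds ratio (1-week versus 6-week) is (0.14/0.86) / (0.18/0.82) = 0.74. For p from 0.10 to 0.30 it is 0.76 to 0.72. With 50% capture in the 1-week arm it is 0.53 to 0.48.

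**The case against.** The strongest reply is that the plan does not rely on recall alone. Patients may report at any time, and serious or troublesome events are the likeliest to arrive that way. The 6-week arm must also recall its own first-week events from about five weeks back, so if most events begin early the arms are nearly alike. Both points stand; they are why the table reaches 1.0 and why the concern is confined to non-serious events that patients do not report.

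It is also fair to say that the diary form itself is not in the documents, so the absence of a symptom item is read from a one-sentence description. The database item for side effects shows an intention to record them, but not prospective collection. Further, the plan names no final test for adverse events, so the only specified between-arm use is the odds-ratio monitoring test.

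Stronger readings that a reader might infer, and that the documents do not support:

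- **Both stopping rules are biased between arms.** The 10% rule pools the arms and counts only serious events judged probably or definitely related. It makes no between-arm comparison.
- **The primary result is affected.** The neurotoxicity scale is completed at baseline and at week 6 and does not depend on adverse-event collection.
- **The odds ratio is inflated 1.2- to 2.6-fold.** Those figures assume no self-reporting and uniform onset, and they measure events captured. The monitored quantity is whether a patient has any treatment-related event. One remembered event is enough to count, and with equal weekly risk the roughly six-fold exposure already puts the true patient-level ratio above 1.

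**Conclusion.** The concern holds in a limited form. Solicited collection happens once, about 33 days after the last on-drug day in the 1-week arm and at about the end of dosing in the 6-week arm. Given any forgetting, and any unreported 6-week-arm events with onset after week 1, capture is lower in the 1-week arm. The direction favours the short course on the adverse-event secondary endpoint and biases the between-arm odds-ratio test.

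The size cannot be derived from the documents. Across the assumptions shown, relative capture lies between 1.0 and 2.6, with about 1.1 to 1.2 if half of events are self-reported promptly and onset is uniform. The result rests on three unknowns: recall decay, the self-reported share and onset timing. It should be corrected at data collection, since events never recorded cannot be recovered in the analysis.

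**What to change.** Add a side-effect line (symptom and onset date) to the diary already dispensed in both arms. At week 6, use it to complete the existing database item on side effects and symptoms, alongside any events reported earlier. Say in the Research Plan that the diary covers symptoms.

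The cost is a slight added burden on patients, a form and database change, and more minor events. Each of those goes to the medical monitor, and the odds-ratio test is repeated after each adverse event, so there is more review and more testing to handle. No extra visit or call is needed.

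This makes recording contemporaneous and alike in both arms. It does not shorten the monitoring delay for unreported events, because the diary is collected only at study completion; removing that delay would need earlier solicited contact at the same times in both arms.

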Coversheet for ClinicalTrials.gov

Title: A shortened antiepileptic drug (AED) course in surgical brain tumor patients: a randomized trial

NCT02334722

Principal Investigator: [name] MD MS

Version Date: 30 October 2019

IRB Protocol

Title: A shortened antiepileptic drug (AED) course in surgical brain tumor patients: a randomized trial

Principal Investigator: [name] MD MS

SubInvestigators: [name] MD, [name] MD

Study Coordinator: [name], BSHS, CCRC

Abstract: Seizures are one of the leading neurologic complications in brain tumor patients. This has led neurosurgeons to use antiepileptic drugs (AEDs) as prophylaxis. However, the drugs are often not withdrawn right away and patients are referred to oncologists for follow-up care. Neither specialty has particular expertise dealing with antiepileptic drugs and as a result, there has been no standardized protocol used to discontinue the drugs and many patients stay on them indefinitely. The result has been considerable practice variation in regard to the use and length of AEDs in the post-operative period². The American Academy of Neurology (AAN) guidelines recommend the discontinuation of Antiepileptic Drugs (AEDs) after the first post-operative week in patients without seizures¹. In an attempt to develop Neurosurgery clinical guidelines for AED use in post-operative brain tumor patients, we will evaluate two different courses of levetiracetam.

Patients who have had a surgical resection of a brain tumor will be randomized to levetiracetam for one week or for six weeks. The primary study endpoint will be performance on a validated neurotoxicity scoring system at 6 weeks post-op. We hypothesize that patients on a shortened AED course (1 week) will have less neurotoxicity as measured by a validated neurotoxicity scoring instrument compared to patients on 6 weeks of treatment. Secondary endpoints will include number of seizures and adverse events. We will also measure medication adherence, and mood alterations to determine if these have any correlation with AEDs.

Version Date: 30 October 2019

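### The primary Mann-Whitney test is valid but ignores the baseline Neurotoxicity score already collected; a rank-based ANCOVA would give a worthwhile gain in power if the baseline-to-6-week correlation is about 0.3 or more

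*Combined protocol and SAP*

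**What the plan says.** The Abstract defines the endpoint as a single 6-week value: "The primary study endpoint will be performance on a validated neurotoxicity scoring system at 6 weeks post-op". The statistical paragraph of the Research Plan names one test for it: "The groups will be compared using the Mann-Whitney test for the neurotoxicity scores". It adds: "The analysis will be performed in an intent-to-treat manner". No covariate, change score or stratification is mentioned.

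The Research Plan also has patients complete the Beck Depression Inventory (BDI) and the Neurotoxicity Scale "at baseline (preoperatively or 24-48hrs postoperatively) and at 6 weeks postoperatively". The Table of Events lists both instruments at both visits, with baseline shown only as 24 to 48 hours post-op.

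Three statements bear on the order of events:
- On the BDI, the exclusion criteria say: "Subjects will have the BDI administered at baseline visit, prior to randomization". No such statement is made for the Neurotoxicity Scale.
- The inclusion criteria require patients to be: "Able to be randomized prior to or up to 48 hours after surgery".
- On study drug, the Research Plan says: "Patients will begin study medication 48 hours post-op, regardless if they are discharged or remain hospitalized".

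**The concern.** The trial has one primary comparison with about 38 patients per arm. Allocation is by simple randomization, so the balance of baseline scores is left to chance. When an outcome is also measured at baseline, adjusting for that value removes the part of the outcome variance it explains. If the two scores are moderately correlated, leaving baseline out costs power and widens the interval around the treatment difference for no saving, since the score is collected anyway.

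Two points decide whether adjustment is safe as well as useful. First, the baseline score should not be influenced by knowledge of the assigned arm. The planned baseline comes before study drug starts, so drug exposure is not the issue, but the order relative to randomization is not stated for this scale. Second, an adjusted analysis that simply drops patients without a baseline score would depart from intent-to-treat and could have less power than the planned test.

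**Working it through.** **Inputs from the documents.** 38 per group, a 5.4-point difference, 80% power, scale maximum 81.

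**Not stated, therefore assumed.** Two-sided 5% test; the SD (back-solved below); r from 0 to 0.7; normal or skewed scores; baselines either all post-op, or half post-op with a 4-point timing shift; 0% or 10% of baselines missing at random.

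**The plan's own figure.** The 38 per group cannot be reproduced directly, because SD, alpha and sidedness are missing. Solving for the SD at two-sided 5%:
- Normal formula: SD = 5.4 / [(1.960 + 0.842) × √(2/38)] = 5.4 / 0.643 = 8.40.
- Noncentral t: the detectable standardized difference is 0.651, so SD = 5.4 / 0.651 = 8.29.
- With the Mann-Whitney efficiency of 3/π: 8.29 × √0.955 = 8.10.

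A one-sided 5% test would give 9.38 by noncentral t. The simulations use 8.29.

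**Analytic effect of adjustment.** Residual variance is multiplied by (1 − r²), with a small-sample penalty of about 1 + 1/72. Break-even is where (1 − r²)(73/72) = 1, so r = √(1/73) = 0.12. Ignoring the penalty, the number per arm for 80% power falls from 38 to 38 × 0.91 = 34.6 (35) at r = 0.3, 38 × 0.75 = 28.5 (29) at r = 0.5, and 38 × 0.51 = 19.4 (20) at r = 0.7.

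**Interval width.** Unadjusted 95% half-width = 1.993 × 8.29 × √(2/38) = 3.79 points. Multiplying by √(1 − r²) gives about 3.6, 3.3 and 2.7 at r = 0.3, 0.5 and 0.7. Allowing for the penalty and the settings below, the ranges are 3.6–3.7, 3.3–3.4 and 2.7–2.9.

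**Simulated power (%), rank-based ANCOVA v Mann-Whitney, complete baselines.** 10,000 trials per setting, 38 per arm, integer scores limited to 0–81; the skewed scores are gamma with an assumed mean of 14, and r is set on the underlying normal scale.

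| r | Normal, all post-op | Normal, mixed timing | Skewed, all post-op | Skewed, mixed timing |
|---|---|---|---|---|
| 0 | 77.9 v 78.1 | 76.5 v 77.3 | 87.1 v 87.5 | 86.4 v 87.3 |
| 0.2 | 78.9 v 77.9 | 79.0 v 78.5 | 88.4 v 87.5 | 87.2 v 87.3 |
| 0.3 | 80.9 v 77.9 | 79.9 v 77.2 | 89.2 v 86.7 | 88.6 v 87.0 |
| 0.5 | 87.2 v 78.4 | 86.4 v 78.1 | 93.6 v 87.3 | 93.4 v 86.6 |
| 0.7 | 95.5 v 77.2 | 95.3 v 78.3 | 98.5 v 87.6 | 98.4 v 86.6 |

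**Power (%) with 10% of baselines missing.**

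| Setting | Median imputation | Complete case | Mann-Whitney |
|---|---|---|---|
| Normal, all post-op, r = 0 | 77.6 | 72.5 | 77.9 |
| Normal, all post-op, r = 0.3 | 80.0 | 75.8 | 77.0 |
| Normal, all post-op, r = 0.5 | 85.9 | 83.2 | 77.4 |
| Normal, mixed, r = 0 | 76.4 | 71.5 | 77.2 |
| Normal, mixed, r = 0.3 | 80.1 | 76.1 | 78.3 |
| Skewed, mixed, r = 0 | 86.3 | 82.2 | 87.1 |
| Skewed, mixed, r = 0.3 | 88.8 | 85.3 | 87.3 |

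The imputation is arm-blind. In the three r = 0 rows, complete-case analysis loses 4.9 to 5.7 points against Mann-Whitney; imputation loses 0.3 to 0.8.

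**Type I error.** Mann-Whitney 4.4–5.6% and rank-based ANCOVA 4.5–5.6% over all null settings.

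**Change scores are no substitute.** In a separate run of 20,000 trials per setting with normal scores, a Mann-Whitney test on change from baseline had 63.9% power at r = 0.3, against 78.3% for the planned test, and only drew level near r = 0.5.

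**The case against.** The strongest objection is that this is a choice between two valid tests, and that the benefit rests on a correlation the documents do not supply. At r = 0.3 the gain is small: at most 3 power points, and a half-width of 3.6–3.7 instead of 3.8. The design may also push r down. Some baselines are taken within two days of surgery, and excluding patients with BDI of 14 or more or perceived cognitive disability may narrow the baseline range. If r is 0.3 for pre-op baselines and 0.1 for post-op ones, half of each, the simulated gain is only 1.0 point; at 0.3 and 0 there is a loss of 0.2. All of this stands and limits the expected benefit. It does not enlarge the downside, which stays below about 1 point.

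The order of baseline and randomization is also less settled than one would like. Because the eligibility BDI must precede randomization and shares the baseline visit, the natural reading is that the Neurotoxicity Scale does too. But randomization may precede surgery while the Table of Events shows only a post-op baseline, and no blinding is described. A sentence added now cannot change the order for patients already scored.

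The narrower interval belongs to a mean-scale model, not to the rank test. With the 5.4-point effect the two disagree on significance in 2.4–5.6% of simulated trials (normal) and 2.8–10.2% (skewed), so the plan must say which one decides. The 3.8-point half-width also depends on the assumed SD; at 9.38 it would be 1.993 × 9.38 × √(2/38) = 4.3.

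Finally, missing 6-week scores need a rule of their own. That is true under either test and is not solved by this change.

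**Conclusion.** The point holds as a recommended improvement, not as a correction. The planned test controls its error rate; the baseline score is collected and not used. Over all settings examined, including 10% of baselines missing with arm-blind imputation, the power change from rank-based ANCOVA is:
- r = 0: a loss of 0.2 to 0.9 points;
- r = 0.2: −0.1 to +1.1;
- r = 0.3: +1.8 to +3.0 with normal scores, about +1.5 to +2.5 with skewed scores;
- r = 0.5: +7.6 to +8.8, or +5.4 to +6.8;
- r = 0.7: +16 to +18, or +10 to +12.

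Gains are smaller under skew because Mann-Whitney power is already about 87% there, against about 78% for normal scores. Thus 0.3 marks a worthwhile gain, not break-even. These figures rest on a two-sided 5% test, SD 8.29 and 38 analysed per arm. Confidence is medium, because r is unknown.

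**What to change.** Before the arms are compared, amend the statistical paragraph as follows:

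- Name one primary analysis: a two-sided 5% rank-based ANCOVA, that is, a linear model of the rank of the 6-week Neurotoxicity score on arm and the rank of the baseline score. Add a pre-op/post-op indicator only if both baseline timings occur.
- Keep every intent-to-treat patient who has a 6-week score. Replace a missing baseline with the overall median, without regard to arm, and code its timing as the reference level.
- State that the rank test decides the primary result. Report an adjusted mean difference in scale points with a 95% CI as descriptive only.
- Keep the unadjusted Mann-Whitney test as a sensitivity analysis.
- State that the baseline Neurotoxicity score is completed before randomization, as is already said for the BDI.

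The cost is a few sentences and one or two degrees of freedom, with no new assessment or patients. The risk is about 1 point of power if r is near 0, provided the missing-baseline rule is adopted. If the arms have already been compared, Mann-Whitney should stay primary.
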